5.3.2 Dose/Treatment Planning Parameters

The CTV (prostate +/- SV) will be treated to dose of 36.25 Gy in 5 fractions. For patients with identifiable DINs, at the physician's discretion, there is an option for a simultaneous integrated boost to PIRADS 3-5 or PSMA avid nodules and/or biopsy positive nodules, delivering 40 Gy to the contoured nodule(s) as a mean dose while respecting normal tissue constraints to rectum and urethra. (If normal tissue constraints to the rectum and urethra can not be achieved, the DIN will be boosted to a lower dose, or not boosted)

Volume of the PTV receiving prescribed SBRT dose should ideally be $\geq 95\%$; acceptable suggested deviation is dose $>85\%$

Critical organ limits (SBRT monotherapy):

1. Rectum: Maximum dose to 1 cc 38.5 Gy, Max dose to 3 cc 34.4 Gy, Max point dose 40 Gy. Acceptable deviation is maximum dose to 1 cc 39 Gy, max dose to 3 cc 36 Gy and max point dose of 42 Gy.
2. Bladder: Maximum dose to 1 cc 38.5 Gy, Max point dose 40 Gy. Acceptable deviation is max point dose of 42 Gy.
3. Penile Bulb: No more than 105% of prescription dose; D3cc 25 Gy. This is a soft constraint.
4. Femoral heads: Maximum point dose 30 Gy
5. Small bowel: Maximum point dose 25 Gy
6. Urethra: Max dose 40 Gy. Will allow up to 42 Gy point dose. Urethra planning organ at risk volume (PRV) can be created around the contoured urethra if there is uncertainty

5.4 Supportive Care Guidelines

- a. Urinary: A proportion of patients undergoing prostate SBRT can expect increase in urinary frequency or urgency. If this becomes bothersome to the patient, medication to alleviate symptoms can be prescribed at the discretion of the treating radiation oncologist and documented in patient chart.

b. Bowel: Bowel symptoms during time of prostate SBRT can occur. If patients develop rectal urgency, tenesmus or diarrhea, medication to alleviate symptoms can be prescribed at the discretion of the treating radiation oncologist, and documented in patient chart.

5.5 Duration of Therapy and Criteria for Removal from Study

In the absence of treatment delays, the SBRT is anticipated to complete within 2-3 weeks time. Patients will undergo radiation 2-3 times a week, but treatment can be slowed down to once a week at the physician's discretion; these differing fractionation patterns fall within standard of care for SBRT. Patients can be removed from the study at any point should they decide they no longer wish to participate. They will continue to receive routine medical care as necessary outside the confines of this study.

Patients will be placed in a prospective database patients undergoing prostate SBRT in our department. As per our usual care, they will fill out I-PSS and EPIC-26 quality of life forms at each follow up visit.

5.6 Duration of Follow Up

Patients will be followed as per standard care. For purposes of this study, patients will be followed with CTCAE evaluation, EPIC-26 quality of life questionnaire, I-PSS scores at each follow up visit (3-6 months; 9-12 months); afterwards they will be prospectively followed as per usual care in the Radiation Oncology department with quality of life questionnaires and adverse event evaluation, I-PSS scores.

6 DOSE MODIFICATIONS

None.

7 ADVERSE EVENT REPORTING REQUIREMENTS

Adverse event (AE) monitoring and reporting is a routine part of every clinical trial. The investigator will be required to provide appropriate information concerning any findings that suggest significant hazards, contraindications, side effects, or precautions pertinent to the safe use of the drug or device under investigation. Safety will be monitored by evaluation of adverse events reported by patients or observed by investigators or research staff, as well as by other investigations such as clinical laboratory tests, x-rays, electrocardiographs, etc.

7.1 Adverse Event Definition

An adverse event (also referred to as an adverse experience) can be any unfavorable and unintended sign (e.g., an abnormal laboratory finding), symptom, or disease temporally associated with treatment, and does not imply any judgment about causality.

Adverse Event Characteristics and Related Attributions

CTCAE term (AE description) and grade: The descriptions and grading scales found in the revised NCI Common Terminology Criteria for Adverse Events (CTCAE) version 4.0 will be utilized for grade 3 or higher AE reporting. A copy of the CTCAE version 4.0 can be downloaded from the CTEP web site (<http://ctep.cancer.gov>).

- **Attribution** of the AE:

- Definite – The AE is *clearly related* to the study treatment.
- Probable – The AE is *likely related* to the study treatment.
- Possible – The AE *may be related* to the study treatment.
- Unlikely – The AE is *doubtfully related* to the study treatment.
- Unrelated – The AE is *clearly NOT related* to the study treatment.

7.2 Recording of Adverse Events

All adverse events will be recorded on a patient specific AE log. The AE log will be maintained by the research staff and kept in the patient's research chart.

7.2.1 Reporting of AE to WCMC IRB

All AEs occurring on this study will be reported to the IRB according to the IRB policy, which can be accessed via the following link:
http://researchintegrity.weill.cornell.edu/forms_and_policies/forms/Immediate_ReportinPolicy.pdf.

7.3 Definition of SAE

SAE's include death, life threatening adverse experiences, hospitalization or prolongation of hospitalization, disability or incapacitation, overdose, congenital anomalies and any other serious events that may jeopardize the subject or require medical or surgical intervention to prevent one of the outcomes listed in this definition.

7.3.1 Reporting of SAE to IRB

All SAEs occurring on this study will be reported to the IRB according to the IRB policy, which can be accessed via the following link:
http://researchintegrity.weill.cornell.edu/forms_and_policies/forms/Immediate_ReportinPolicy.pdf.

7.4 Expedited Adverse Event Reporting

The principal investigator is responsible for monitoring the safety of patients who enroll in the study. All AEs occurring after treatment will be followed until resolution. The descriptions and grading scales found in the revised NCI CTCAE version 4.0 will be used for adverse event reporting. A copy of the CTCAE version 4.0 can be downloaded from the CTEP web site (<http://ctep.cancer.gov/reporting/ctc.html>).

A serious adverse event (SAE) is any adverse experience that results in any of the following outcomes:

- Death.
- Life-threatening adverse experience.
- Requires inpatient hospitalization or prolongation of existing hospitalization.
- Persistent or significant disability/incapacity.
- A congenital anomaly/birth defect.
- Important medical events: Defined as AEs that, based upon appropriate medical judgment, may jeopardize the patient and may require medical or surgical intervention to prevent 1 of the outcomes listed above, even though these events may not be immediately life-threatening or result in death or hospitalization.

All SAEs occurring on this study will be reported to the IRB according to the IRB policy, which can be accessed via the following link:

http://researchintegrity.weill.cornell.edu/forms_and_policies/forms/Immediate_Reportin_Policy.pdf

7.4.1 AE/SAE Follow Up

All SAEs and AEs reported during this study will be followed until resolution or until the investigator confirms that the AE/SAE has stabilized and no more follow-up is required. This requirement indicates that follow-up may be required for some events after the patient discontinues participation from the study.

8 PHARMACEUTICAL INFORMATION

There is no investigative agent used on this protocol.

9 CORRELATIVE/SPECIAL STUDIES

9.1 Correlative Study: Blood draws for immune correlates and microbiome collection

Patients will provide blood draw prior to, at the completion of radiation and at 3-6 months post treatment follow up. They will also be providing a stool sample for microbiome analysis at baseline, end of completion and 3-6 month follow up (last stool sample is optional). This is a correlative study.

Blood Sample Collection and Procedure

Blood samples (40-ml) will be collected in heparinized “Green Top” tubes (for PBMC and plasma isolation) and processed within 4 h of sample receipt. The PBMC will be isolated using a 1.077 g/ml Ficoll layer to enrich the leukocytes and remove the dead cells and any red cells, and cryopreserved in 10% DMSO, 90% human AB serum at 10×10^6

cells/vial and stored in liquid nitrogen for batch analysis. Plasma will also be aliquoted and stored at -80°C for batch analysis. We anticipate analyses of T cell subsets and neutrophil/lymphocyte ratios, as well as cytokine measurement and proliferation analyses (all markers of peripheral immune correlates to assess status over time).

Microbiome collection

Collection of Specimen(s): Patients will be provided with a stool collection container and be instructed on providing a specimen appropriately, which can be done from home or in the clinic.

Handling of Specimens(s): Samples received will be promptly frozen at 20 degrees C, and transferred within the next week to a -80 degree freezer or liquid nitrogen for long-term storage. DNA extractions and 16sRNA analysis will be performed once all samples are collected.

The microbial DNA will be isolated and used to provide DNA sequence information. We will perform taxonomic characterization of bacteria (using 16S rRNA). Prokaryotic diversity will be screened using massively parallel DNA sequencing, exploiting a multiplexing technique to generate 16S rRNA sequence tags, followed by analyses (statistical, clustering, and phylogenetic) to estimate the distribution of phylotypes, differential abundance, and the relative contributions between phylotypes and community dissimilarities to the overall diversity in individuals.

We will examine whether there are metagenome sequence content changes during radiation treatment, and study whether differences in gene content indicate differences in functional pathways between the normal and irradiated microbiome using pathway analysis.

Samples will be collected by the research team and the samples will be stored in -80C freezer in [name] lab until sample analysis.

10 MEASUREMENT OF EFFECT

This is a safety study.

Treatment will be deemed safe if there are no more than 3 acute greater than grade 3 radiation treatment related GI/GU adverse events within 3-6 months of treatment (CTCAE 5.0 criteria).

The primary endpoint will be safety, as measured by the percentage of treatments that are delivered without radiation treatment related GI/GU toxicity within 3-6 months from start of treatment. Given that the treatment plans will meet standard normal tissue constraints used for SBRT, and rigorous safety metrics need to be met before radiation is delivered, we do not anticipate any increased toxicity on this study compared to standard SBRT.

11 DATA REPORTING / REGULATORY CONSIDERATIONS

11.1 *Data Collection*

The data collection plan for this study is to utilize REDCap to capture all treatment, toxicity, efficacy, and adverse event data for all enrolled patients.

11.2 *REDCap*

REDCap (Research Electronic Data Capture) is a free data management software system that is fully supported by the Weill-Cornell Medical Center CTSC. It is a tool for the creation of customized, secure data management systems that include Web-based data-entry forms, reporting tools, and a full array of security features including user and group based privileges, authentication using institution LDAP system, with a full audit trail of data manipulation and export procedures. REDCap is maintained on CTSC-owned servers that are backed up nightly and support encrypted (SSL-based) connections. Nationally, the software is developed, enhanced and supported through a multi-institutional consortium led by the Vanderbilt University CTSA.

11.3 *Regulatory Considerations*

All protocol amendments and consent form modifications will be made by the Principal Investigator.

11.4 *Data Management*

All patient data will be entered and maintained in REDCap. These data include clinical data and all patient safety data. The REDCap provides audit trails that track creation and modification of records that include user id and timestamp. Once entered, the data is subjected to validation procedures that are executed either immediately or upon saving the eCRF page or during the batch validation process. Validation failures that are identified before the page is saved can be corrected immediately. Validation failures during saving of the eCRF page and during batch validation processes will generate a discrepancy. Depending on the database account privileges, the data managers may be able to correct a discrepancy or if not, route it to the project data manager at WCMC who can take appropriate action to correct the problem. Data clarification forms can also be printed out when necessary to be sent to the project data manager at JCTO. Once the discrepancy is closed, by marking “resolved” or “irresolvable”, the data is marked clean and an audit trail is generated by the system.

All key end points will be source verified by a second person at each site and errors will be corrected. Once the data is verified and all discrepancies are closed, the data can be locked/frozen. Locking and freezing can be done at different granular levels and will follow institutional SOPs and any specific requirements for the project.

Security measures that will be taken in order to protect patient data will include firewall technology and database level security which will be achieved by assigning roles and

privileges to different levels of users and by requiring that the users authenticate themselves using user id and password. Additional security for data transfer between remote clients and servers will be achieved by using digital certificates/SSL. All data will be backed-up to tape periodically according to the Institutional SOPs. All data will be stored for at least 5 years following the termination of this study.

12 STATISTICAL CONSIDERATIONS

12.1 *Study Design/Endpoints*

12.1.1 Primary Objectives

Safety of this approach will be determined by assessing acute GI/GU toxicity (CTCAE 5). The treatment will be deemed safe if no more than 3 patients experience a grade 4 likely radiation treatment related GI/GU (or higher) adverse event within 3-6 months from the end of treatment.

12.1.2 Secondary Objectives

Secondary objectives include quality of life (HRQOL) measures including: 1) the Expanded Prostate Cancer Index Composite (EPIC) short form questionnaire, 2) International Prostate Symptom Score (I-PSS). These will be assessed at baseline, at the 3-6 month follow-up visit and at the 9-12 month follow-up visit.

Toxicity data will also be assessed at 3-6 months and at 9-12 months follow up visit using CTCAE criteria.

12.1.3 Correlative Study Objectives

Microbiome and labs will be collected for exploratory analyses to see how radiation impacts the host microbiome and peripheral immune correlates found in blood.

12.2 *Sample Size/Accrual Rate*

We plan to accrue 20 patients over 2 years, or about 4-6 patients every 6 months.

12.3 *Analysis of Primary and Secondary Endpoints*

Primary Endpoint:

The treatment will be deemed safe if the grade 4+ likely radiation treatment related GI/GU adverse event rate is less than 10% within 3-6 months of the end of treatment. The proportion of patients that experience a >grade 3 GU/GU adverse event will be determined with a binomial

point estimate and corresponding exact 95% binomial confidence interval. If the lower bound of the interval is below 10%, the treatment will be considered safe.

Secondary Endpoints:

QOL measures at baseline and at follow up (3-6 months post treatment start, and 9-12 months) will be summarized numerically and graphically using mean (sd), median (interquartile range), or count (percent) as appropriate, and 95% confidence intervals estimated where possible. The QOL value will be plotted over time with a line for each patient and a smoothed curve superimposed on the plot. Changes in scoring from pre- to post-treatment will also be determined. EPIC-26 overall scores as well as domain summary scores (urinary incontinence, urinary irritative/obstructive, bowel, sexual, hormonal) and individual item responses will be evaluated. Similarly, overall score as well as individual item responses will be assessed for the I-PSS survey.

Toxicity will be assessed using CTCAE 5.0 criteria at 3-6 months and 9-12 months.

These analyses will be descriptive.

Correlative study endpoints:

Microbiome

Statistical analysis of microbiome and metagenome composition will be performed in the R statistical programming environment using package *phyloseq*, which incorporates and builds upon community ecology packages such as *ade4* and *vegan* and employs the flexible graphic system *ggplot2*, to easily visualize complex data relationships. For 16S data, we will evaluate the adequacy of sequencing efforts using rarefaction plots. Alpha diversity index for each will be characterized through dominance, equitability, richness, evenness. The diversity metrics will be calculated at OTU and higher taxonomical levels to best characterize the community structure. We will test for associations of each of these alpha diversity metrics with the time relative to radiation exposure, using one-way ANOVA after even-sampling the observations to a depth cut-off maximizing the number of samples and depth. In addition, rank-abundance plots will be used to visualize differences in abundance of dominant taxa in the clinical and phenotypic groups. We will utilize skyline plots to visualize the patterns of community structure in terms of relative abundances in the collected samples between before and after the radiation treatment. Similarly, for metagenomic data, skyline plots will be used to reveal functional compositions of the samples. Heat-maps will be plotted to visualize clustering patterns in the data.

We will study the evolution of microbiome over time as a consequence of the radiation treatment. The relative abundances at each taxonomical level will be first normalized by log-ratio transformation. Then the transformed relative abundance of each individual taxa at multiple time points will be fitted by the linear mixed model along with the time effect and all subject-specific characteristics as the independent covariates. For the nonlinear trend, we will combine the nature splines with linear mixed model in the data analysis. The same model will be applied on the indices calculated in the ecology microbial analysis.

CBC collection

Plasma samples will be collected at three time points: before radiation, following completion, and 3-6 months after completion. We hope to understand the impact of radiation on the distribution and frequency of peripheral immune mediators at these time points. To this effect, NLR will be numerically and graphically summarized in several ways. The average ratio at each time will be estimated, as well as average changes from baseline, and individual trajectories will be plotted in “spaghetti plots.” Parallel summaries will be presented dichotomizing N/L ratio at 4%, counting the proportion of patients above this threshold at each time point.

Several markers beyond N/L ratio are of interest in order to thoroughly characterize changes throughout radiation treatment, including continuous (e.g. T cell panel and TREG panel, IL-7, IL-15, IL-6, IL-10, IL-17, IL-2 cytokines), and categorical (e.g. proliferative ability) measures. These will be summarized and analyzed in an exploratory manner in parallel methods to N/L ratio, if funding is secured for these analyses.

13 Data and Safety Monitoring Plan (DSMP)

The WCMC Data and Safety Monitoring Committee (DSMC) is the central monitoring board for this study.

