SBRT	Stereotactic Body Radiation Therapy
SHIM	Sexual Health Inventory Men
SIB	Simultaneous integrated boost
STAMPEDE	Radiotherapy to the primary tumour for newly diagnosed, metastatic prostate cancer
SUSAR	Suspected Unexpected Serious Adverse Reaction
TRUS	Transrectal Ultrasound
UAP	Unanticipated Problem
WCMC	Weill Cornell Medical College

Summary of changes for version 5.0 dated 26JUL2023

Sections	Change	Rationale
Principal Investigator section	Changing Principal investigator from [name] to [name]	Changing Principal investigator from [name] to [name], since [name] will no longer be at WCM.
No changes to the Informed consent since the study is closed to accrual and only in follow up.		

Summary of changes for version 4.0 dated 03FEB2022

Sections	Change	Rationale
Primary Objective	Revising the toxicity measurement timeframe stated in the primary objective from 30 days to 3-6 months post treatment.	Revising the toxicity measurement timeframe stated in the primary objective from 30 days to 3-6 months post treatment and keep it consistent with the study calendar.
Personnel changes	Adding [name] to the protocol cover page.	Updating personnel and contact information. Admin amendment approved on 16NOV2021.
No changes to the Informed consent		

Summary of changes for version 3.0 dated 05OCT2021

Sections	Change	Rationale
Principal Investigator section	Changing Principal investigator from [name] to [name]	Changing Principal investigator from [name] to [name]
Personnel changes	Removed [name] as Nurse practitioner and [name] as study coordinator, Added [name]. Updated contact details for personnel.	Change of personnel and contact information.
Informed consent changes		
Principal Investigator section	Changing Principal investigator from [name] to [name]	Changing Principal investigator from [name] to [name]

Summary of changes for version 2.0 dated 24JAN2020.

1. **Inclusion Criteria:** Must have metastatic prostate cancer proven on biopsy or imaging
2. **Exclusion Criteria:** Removing criteria # 4 - Evidence of disease progression on bone scan, MR and/or CT
3. Revised accrual ceiling to 25 patients as stated in the IRB application
4. Adding [name] as data manager to the protocol to keep it consistent with the IRB personnel list.
5. Updating QOL – AUA to I-PSS
6. Study Calendar – clarifying that blood/stool collection is optional at all time points as stated in the informed consent.

Informed consent changes:

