1. The protocol version date is incorrect - changing the footer of the informed consent.
2. Making study calendar consistent with the protocol.

Document History

Document Name	Version number	Version Date
Amendment 4	5.0	26JUL2023
Amendment 3	4.0	03FEB2022
Amendment 2	3.0	05OCT2021
Amendment 1	2.0	24JAN2020
Initial Protocol	1.0	23JUL2019

Protocol Summary

PRAGMA (Prostate Radio Ablation Guided by Magnetic resonance imaging Acquisition) in metastatic prostate cancer

IRB Protocol #: 19-04020263

Short Title:	MRI-guided prostate SBRT for metastatic prostate cancer
Principal Investigator:	[name]
Sample Size:	N = 20
Accrual Ceiling:	This study plans to enroll a total of 25 patients
Study Population:	Patients with metastatic prostate cancer
Accrual Period:	2 years
Study Design:	Single-arm study for safety

Study Intervention Description:

MR-guided Prostate SBRT:

Prostate SBRT has become a standard of care for the treatment of localized prostate cancer. Radiation is delivered to the prostate and seminal vesicles in 5 treatment sessions (fractions). Doses ranging from 35-45 Gy in 5 fractions have demonstrated good outcomes with acceptable toxicity when planning is delivered appropriately.

There is emerging evidence that patients with *non*-localized prostate cancer also derive benefit from radiation (RT) to the primary tumor. The STAMPEDE multiarm British trial recently reported that patients with low burden metastatic prostate cancer have an overall survival benefit from prostate RT. Doses of radiation used in the STAMPEDE trial were either 36 Gy in 6 fractions, or 55 Gy in 20 fractions.

The MRidian ViewRay offers delivery of prostate SBRT with real-time MR guidance, which provides superior soft-tissue differentiation with excellent visualization of the prostate. This ViewRay platform offers the ideal setting for this study, that aims at precisely delivering prostate SBRT with a simultaneous integrated boost (when indicated) to visible nodules.

In this study, we hope to demonstrate the safety of using 36.25 Gy in 5 fractions, plus a simultaneous integrated boost (when indicated), in patients with metastatic prostate cancer.

Hypothesis: Patients with metastatic prostate cancer can undergo MRI-guided prostate SBRT without significant adverse events, similar to what has been reported for patients with localized prostate cancer.

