1.1 Primary Objectives

1.11 To assess safety of delivering MRI-guided prostate SBRT in patients with metastatic prostate cancer.

Treatment will be deemed safe if there is no more than 3 acute >G3 likely radiation treatment related GI/GU toxicity within 3-6 months after treatment (CTCAE 5.0 criteria) completion. Given that the treatment plans will meet rigorous normal tissue constraints used for standard prostate SBRT that have been established now with up to 10 year follow up data in patients with localized prostate cancer, we do not anticipate any increased toxicity on this study for metastatic prostate cancer patients.

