The goal of this study is to assess safety of treating patients with metastatic prostate cancer with MRI-guided prostate SBRT. Safety is defined as lack of more than 3 patients with treatment related acute >G3 GI or GU toxicity within 3- 6 months post treatment. The proposed SBRT dose (36.25 Gy in 5 fractions to the whole prostate) has been reported in the literature to be safe and well tolerated (Table 2), with no acute G3 toxicity. The proposed boost dose to 40 Gy in applicable patients is within the range of current standard of care SBRT doses, and is also expected to be well-tolerated. Furthermore, it has been tested in our currently ongoing investigator initiated protocol in patients with non-metastatic prostate cancer (“MRI-guided Stereotactic Body Radiotherapy (SBRT) with Simultaneous Integrated Boost for Prostate Cancer” PI: [name], [name] IRB Protocol # 1802019010). As of 4/29/19, 15 patients with localized prostate cancer have enrolled on this study with planned accrual of 30 patients, and have demonstrated excellent safety and feasibility with boost doses up to 45 Gy. It

is therefore expected that similar outcomes can be achieved in patients with metastatic prostate cancer, though it is possible that the addition of systemic therapy may alter likelihood of toxicity.

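### Section 12.3 declares SBRT safe when the lower exact 95% bound is below 10%; this cannot show a rate below 10%, and it contradicts the limit of three patients

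*Combined protocol and SAP*

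**What the plan says.** The primary-endpoint paragraph of Section 12.3 first sets the target: "The treatment will be deemed safe if the grade 4+ likely radiation treatment related GI/GU adverse event rate is less than 10" per cent, within 3-6 months of the end of treatment. It then calls for the proportion of patients with an event above grade 3, with an exact 95% binomial interval, and ends with the decision rule: "If the lower bound of the interval is below 10%, the treatment will be considered safe".

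The final safety criterion appears elsewhere in other forms:

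- Section 12.1.1 deems treatment safe if at most 3 patients have a likely related GI/GU event of grade 4 or higher. Section 2.7 agrees: "Safety is defined as lack of more than 3 patients with treatment related acute >G3 GI or GU toxicity".
- The Protocol Summary and Section 1.1 apply the limit to toxicities: "Treatment will be deemed safe if there is no more than 3 acute >G3 likely radiation treatment related GI/GU toxicity".
- Section 10 applies it to events: "Treatment will be deemed safe if there are no more than 3 acute greater than grade 3 radiation treatment related GI/GU adverse events". The same section also describes the primary endpoint as the percentage of treatments delivered without related GI/GU toxicity, with no grade given and with time counted from the start of treatment.

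The planned sample size is 20 (Protocol Summary and Section 12.2). The accrual ceiling line reads "This study plans to enroll a total of 25 patients". The summary of changes for version 5.0 records that "the study is closed to accrual and only in follow up". The number actually treated is not given.

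**The concern.** The decision sentence looks at the wrong end of the interval. To support a claim that the rate is below 10%, the data must exclude rates of 10% and above, and that is a statement about the upper bound. A lower bound below 10% means only that the data have not shown the rate to exceed 10%. Small samples meet that condition easily because their intervals are wide, so the less information the trial has, the easier it is to pass.

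The sentence also competes with the limit of three patients. Both use the same grade (above 3, which is 4 or higher), the same organ systems and a 3-6 month window, so definitions do not explain the difference. The plan names no governing rule.

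This is the only primary endpoint. Following Section 12.3 as written, a report could call treatment safe with a quarter of patients having grade 4+ toxicity, while Section 12.1.1 calls the same result not safe.

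**Working it through.** **Inputs.** From the documents: n = 20 (Section 12.2), ceiling 25 (Protocol Summary), exact 95% binomial interval and 10% threshold (Section 12.3), limit of 3 patients (Sections 2.7 and 12.1.1). The interval is taken as two-sided. The plan gives no error rates, power or assumed event rate, so it has no design figure to reproduce. All true rates below are assumptions.

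**Step 1: exact intervals.** For x affected of n, the Clopper-Pearson bounds are lower = Beta quantile(0.025; x, n − x + 1) and upper = Beta quantile(0.975; x + 1, n − x).

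| Affected | Observed | Exact 95% interval | Lower bound < 10% | At most 3 patients | Observed < 10% |
|---|---|---|---|---|---|
| 0/20 | 0% | 0.0% to 16.8% | safe | safe | safe |
| 1/20 | 5% | 0.1% to 24.9% | safe | safe | safe |
| 2/20 | 10% | 1.2% to 31.7% | safe | safe | not safe |
| 3/20 | 15% | 3.2% to 37.9% | safe | safe | not safe |
| 4/20 | 20% | 5.7% to 43.7% | safe | not safe | not safe |
| 5/20 | 25% | 8.7% to 49.1% | safe | not safe | not safe |
| 6/20 | 30% | 11.9% to 54.3% | not safe | not safe | not safe |

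The lower-bound rule and the limit of three conflict at exactly 4 and 5 of 20. If the 10% target is instead read as a separate criterion on the observed rate, the disagreement covers 2 to 5.

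**Step 2: other numbers treated.** The lower-bound rule accepts up to 5 for n = 20 to 23 and up to 6 for n = 24 to 25 (6/25: 9.4% to 45.1%; 7/25 has lower bound 12.1%). The conflict with the limit of three is therefore at 4-5 for n = 20 to 23 and at 4-6 for n = 24 to 25. On the observed-rate reading, where at most 2 pass for n = 21 to 25, the range is 3-5 for n = 21 to 23 and 3-6 for n = 24 to 25.

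**Step 3: how often the rules disagree.** With X ~ Binomial(n, p), P(conflict) = P(X ≤ c) − P(X ≤ 3), where c = 5 at n = 20 and 6 at n = 25. The observed-rate reading replaces P(X ≤ 3) by P(X ≤ 1) at n = 20 and P(X ≤ 2) at n = 25. These figures assume that all n patients are treated and ignore the Section 13.2 accrual pause, so they describe the criteria and not the whole trial.

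| True rate (assumed) | n = 20: 4-5 | n = 20: 2-5 | n = 25: 4-6 | n = 25: 3-6 |
|---|---|---|---|---|
| 1% | 0.004% | 1.7% | 0.01% | 0.2% |
| 2% | 0.06% | 6.0% | 0.14% | 1.3% |
| 5% | 1.6% | 26.4% | 3.4% | 12.7% |
| 10% | 12.2% | 59.7% | 22.7% | 45.3% |
| 20% | 39.3% | 73.5% | 54.6% | 68.2% |

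Probability of a safe verdict at a true rate of 20%:

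| Criterion | n = 20 | n = 25 |
|---|---|---|
| Lower bound < 10% | 80.4% | 78.0% |
| At most 3 patients | 41.1% | 23.4% |
| Observed rate < 10% | 6.9% | 9.8% |

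**Step 4: would the upper bound work as the test?** With zero events the two-sided upper bound is 1 − 0.025^(1/n). This gives 16.8% at n = 20 and 13.7% at n = 25, and it first falls below 10% at n = 36 (9.7%). No result from 20 or 25 patients could pass.

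**Step 5: unit of count.** One patient with four qualifying events fails the limit in the Protocol Summary and Sections 1.1 and 10, which count toxicities or events. The same patient passes Sections 2.7 and 12.1.1, which count patients.

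**The case against.** The best case on the other side has three parts.

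First, Section 13.2 suspends accrual once more than 2 patients have a grade 4 likely related event, and the trial is then modified or terminated. High counts are therefore less likely than Step 3 shows. As an illustration, assume 20 patients evenly spaced over 24 months, event onset uniform over 3 or 6 months, and accrual ending for good at the third event. At a true rate of 20% the conflict probability then falls from 39.3% to about 7% (3-month onset) or 15% to 16% (6-month onset). At 10% it falls from 12.2% to about 2% or 4%. This is close to the largest effect the pause could have; if accrual resumes, the reduction is smaller. The objection reduces the size of the problem but does not remove it. The pause does not set the final verdict, and events can appear after further patients have been treated.

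Second, the documents expect little toxicity. Section 2.7 cites no acute grade 3 toxicity at this dose, and Table 2 lists grade 3 or higher rates of 0% to 4.4% per organ system. At a true grade 4+ rate of 1% to 2%, 0 or 1 of 20 affected has probability 98.3% to 94.0%, and all three patient-level readings agree there. That is right as far as it goes. But Table 2 concerns localized disease, no grade 4+ rate is given, and Section 2.7 itself says systemic therapy may alter the likelihood of toxicity. A low rate cannot be assumed in the study meant to test it.

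Third, the limit of three appears in five places and the lower-bound sentence in one, so the limit is arguably the intended definition. The 2-5 and 3-6 ranges also depend on treating the 10% target as a separate criterion, and they should carry less weight. Both points are fair. Even so, the sentence stands in the section that specifies the primary analysis, and nothing subordinates it.

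**Conclusion.** The concern holds. Followed as written, Section 12.3 can call treatment safe with up to 5 of 20 or 6 of 25 patients affected, and the result would not show a rate below 10%. It contradicts the limit of three patients at 4-5 of 20 and 4-6 of 25. These ranges rest only on a two-sided exact 95% interval and the number treated.

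The practical effect depends on the unknown grade 4+ rate: negligible at 1% to 2% and substantial at 10% to 20%, though smaller once the accrual pause is taken into account. Neither 20 nor 25 patients can show a rate below 10% at two-sided 95% confidence, even with no events. It needs correcting before the primary result is reported, because it is the only primary decision rule and its sentence cannot support its stated conclusion.

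**What to change.** - Delete the lower-bound sentence from Section 12.3.
- Reconcile the Protocol Summary and Sections 1.1, 2.7, 10, 12.1.1 and 12.3 into one final criterion chosen by the sponsor. State it as a number of patients, with the observed rate it implies at the number actually treated. A limit of 3 is 15% of 20 or 12% of 25, so it is not consistent with an observed rate below 10% at either size; 2 is 10% of 20 or 8% of 25. Include the second endpoint definition in Section 10 (no grade, timed from the start of treatment) so that no competing endpoint remains.
- Report the proportion with its two-sided exact 95% interval, and present the upper bound as the highest rate compatible with the data. State that the sample cannot demonstrate a rate below 10% at that confidence level.
- Ask the sponsor to confirm that the accrual-suspension rule in Section 13.2, which covers any likely related grade 4 event, is meant to differ from the final criterion.
- Record whether the change came before review of the primary toxicity data. If it did not, label it post hoc and report the verdict under each criterion now in the plan, side by side.

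The cost is text edits and a more modest claim, with no extra patients or data. The documents do not say whether the toxicity data have been reviewed, so a post hoc declaration may be unavoidable.
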